7 EFFICACY ASSESSMENTS

7.1 Primary Efficacy Parameter

The primary efficacy parameter is the proportion of patients with an overall success (clinical cure and microbiologic eradication) in the m-MITT Population at the TOC Visit.

7.2 Secondary Efficacy Parameters

The secondary efficacy parameters include the following:

- Proportion of patients with a response of clinical cure in the Modified Intent-to-Treat (MITT), m-MITT, Clinical Evaluable (CE), and Microbiologic Evaluable (ME) Populations at the TOC Visit; and
- Proportion of patients with a response of microbiologic eradication in the m-MITT and ME Populations at the TOC Visit.

7.3 Other Efficacy Parameters

The exploratory efficacy parameters include the following:

- Proportion of patients with a response of sustained microbiologic eradication in the m-MITT and ME Populations at the LFU Visit;
- Proportion of patients with a response of sustained clinical cure in the MITT, m-MITT, CE, and ME Populations at the LFU Visit;
- Proportion of patients with a response of clinical cure in the MITT and m-MITT Populations at Day 5;
- All-cause mortality through the LFU Visit in the MITT Population;
- Summary (number and percentage of patients) of the assessment of clinical signs and symptoms of cUTI and AP at each time point throughout the study by treatment group in the MITT Population; and
- Descriptive statistics of the length of hospital stay by treatment group for the MITT Population.

7.4 Overall Response

The primary efficacy outcome is a composite outcome (overall response) and is programmatically determined based on the clinical and microbiologic outcomes (see Sections 7.6 and 7.8, respectively) as 1 of the following overall responses:

Overall success: a patient who is deemed a clinical cure AND who achieved microbiologic eradication.

Overall failure: a patient who is deemed a clinical failure OR is deemed to have microbiological persistence.

Overall indeterminate: insufficient data are available to determine if the patient is an overall success or failure.

7.5 Assessment of Clinical Signs and Symptoms

Clinical signs and symptoms will be assessed at Screening, daily during IV treatment beginning on Day 2, at the EOT Visit, at the TOC Visit, and at the LFU Visit. When possible, the same study personnel should complete the assessments at approximately the same time each day. Maximum daily temperature (defined as the maximum temperature reported on a single calendar day) will be recorded. Body temperature may be taken per the site's preferred method and will be recorded in the appropriate eCRF. The same method of measuring a patient's body temperature should be used throughout the study.

The following signs and symptoms will be assigned a classification of absent, mild, moderate, or severe:

- Urinary frequency,
- Urinary urgency,
- Dysuria,
- Nausea,
- Vomiting,
- Abdominal pain,
- Suprapubic pain or discomfort,
- Flank pain, and
- Costo-vertebral angle tenderness.

7.6 Clinical Outcome

Based on the assessment of signs and symptoms, the Investigator will choose 1 of the following clinical outcomes at the Day 5, EOT, and TOC Visits:

Clinical cure: complete resolution or significant improvement of signs and symptoms of cUTI or AP that were present at baseline and no new symptoms, such that no further antimicrobial therapy is warranted.

Clinical failure: symptoms of cUTI or AP present at study entry have not significantly improved or completely resolved, or new symptoms of cUTI or AP have developed and require the initiation of a non-study antibacterial drug therapy, or death.

Clinical indeterminate: insufficient data are available to determine if the patient is a cure or failure.

Based on the assessment of signs and symptoms, the Investigator will choose 1 of the following clinical outcomes at the LFU Visit:

Sustained clinical cure: met criteria for clinical cure at the TOC Visit and the LFU Visit.

Relapse: clinical cure at the TOC Visit but signs and symptoms of cUTI or AP are present at the LFU Visit.

Clinical failure: clinical failure at the TOC Visit carried forward to the LFU Visit or death between the TOC Visit and LFU Visit.

Clinical indeterminate: insufficient data are available to determine if the patient is a sustained clinical cure or clinical relapse.

Note: if a patient is a clinical failure at EOT, the patient is automatically considered a failure at the TOC and LFU Visits, and an assessment of clinical response by the Investigator will be listed as “failure at EOT.”

7.7 Microbiologic Assessments

Urine culture samples will be obtained at Screening or Day 1, Day 5, Day 7, the EOT Visit, the TOC Visit, the LFU Visit, and any time the patient is deemed to have failed while on therapy. In patients with concurrent bacteremia who receive blinded study drug on Day 8 to Day 14, urine culture samples will be obtained daily. Urine cultures will be performed by the local laboratory. Additionally, a urinalysis including urine dipstick analysis for leukocytes, nitrites, or a catalase test of the urine specimen, microscopic evaluation, specific gravity, and pH will be performed at Screening, Day 1, Day 3, Day 7, the EOT Visit, the TOC Visit, and the LFU Visit. Screening urinalysis will be performed by the local laboratory; all other urinalysis samples will be sent to the central laboratory.

A urine sample taken to support diagnosis or to treat a medical condition within 48 hours prior to the first dose of study drug can be used for baseline microbiologic assessments if the organism(s) cultured were obtained and stored for shipment to the designated central laboratory. Otherwise, a repeat urine sample for baseline microbiologic assessments is required.

A repeat urine sample for culture must be obtained prior to the start of study drug treatment for any patient enrolled in the study who has received a single dose of a short-acting antibiotic in the 24 hours prior to randomization or for patients who failed preceding antimicrobial therapy. This sample should be taken as close to randomization as possible (within 2 hours prior to randomization, if possible).

Urine culture samples must be obtained through 1 of the following methods that minimizes the risk of bacterial contamination:

- Clean-catch mid-stream,
- Newly-inserted Foley catheter (bag specimens are not permitted),
- Bladder needle aspiration, or
- Ureter aspiration.

Baseline urine cultures must grow 1 or 2 bacterial organisms, each at $\geq 10^5$ CFU/mL. If a patient grows ≥ 3 organisms in the urine, the urine culture will be considered contaminated unless ≥ 1 of the organisms also grows in a concurrently obtained blood culture.

Two sets of blood culture samples must be obtained from 2 separate venipuncture sites at Screening. Each set is collected from a separate venipuncture and consists of 1 aerobic and 1 anaerobic blood culture bottle. Each set of blood cultures should be collected by direct venipuncture from independent sites approximately 15 to 30 minutes apart. If baseline blood cultures are positive and not considered contaminated, repeat blood cultures should be obtained daily until negative or if the patient is a treatment failure. To avoid unnecessary blood draws, the

Investigator may wait until the result of the prior blood culture is known before performing the next blood culture.

The local laboratory will culture each sample for organism identification, quantification (urine only), and susceptibility testing. Any organism isolated from the blood or urine will be identified by genus and species by the local laboratory. Potential pathogen(s) cultured at the local laboratory from urine or blood samples will be sent to a designated central laboratory for confirmation of identification and susceptibility testing results.

Only those baseline potential pathogens that grow in the urine at $\geq 10^5$ CFU/mL and deemed not to be contaminants will be sent to the central laboratory. Potential pathogens that grow in both the urine and blood will also be sent to the central laboratory prior to randomization.

For post-baseline urine cultures, only those potential pathogens that grow at $\geq 10^3$ CFU/mL and deemed not to be contaminants will be sent to the central laboratory.

Although local susceptibility testing is not a requirement, when local susceptibility testing indicates non-susceptibility to imipenem (eg, intermediate susceptibility or resistance to imipenem) but the patient is stable or clinically improving, the patient should remain on study drug at the discretion of the Investigator. Prior to discontinuation from study drug, the Investigator should discuss such cases with the Medical Monitor.

When a patient's urine culture grows only Gram-positive organisms, but the patient is clinically improving, the patient may remain on study drug without additional Gram-positive antibiotic coverage at the Investigator's discretion. Patients who are not clinically improving should be discontinued from study drug at the discretion of the Investigator but should remain in the study to complete all study assessments.

7.8 Microbiologic Outcome

Per-patient microbiological response is determined programmatically based on the results of blood and urine cultures as 1 of the following outcomes at the Day 5, EOT, and TOC Visits:

Microbiologic eradication: the demonstration that the baseline bacterial pathogen(s) is reduced to $< 10^4$ CFU/mL according to the Food and Drug Administration (FDA) criteria and $< 10^3$ CFU/mL according to the European Medicines Agency (EMA) criteria on urine culture and negative on repeat blood culture (if positive at baseline).

Microbiologic persistence: the urine culture grows $\geq 10^4$ CFU/mL for the FDA ($\geq 10^3$ CFU/mL for the EMA) of any of the baseline pathogen(s) identified at study entry and/or a blood culture demonstrates the same baseline pathogen(s). Patients who are a persistence at EOT will be considered a persistence at TOC.

Microbiologic indeterminate: no follow-up urine culture is available, or the follow-up urine culture cannot be interpreted for any reason, or the follow-up urine culture is considered contaminated. For a baseline blood pathogen, no follow-up blood culture is available.

Per-patient microbiological response is determined programmatically based on the results of blood and urine cultures as 1 of the following outcomes at the LFU Visit:

Sustained microbiologic eradication: microbiologic eradication at the TOC Visit and the LFU Visit.

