Although local susceptibility testing is not a requirement, when local susceptibility testing indicates non-susceptibility to imipenem (eg, intermediate susceptibility or resistance to imipenem) but the patient is stable or clinically improving, the patient should remain on study drug at the discretion of the Investigator. Prior to discontinuation from study drug, the Investigator should discuss such cases with the Medical Monitor.

Day 1 is defined as the first day of study drug administration. The subsequent study days are defined by the number of calendar days thereafter. The duration of antibiotic treatment with study drug therapy will be 7 days (28 doses), with a prolongation of therapy up to 14 days if clinically indicated in patients with concurrent bacteremia.

All patients should receive at least 8 doses of IV study drug before the Investigator considers the patient to be a clinical failure and discontinues the patient from study drug therapy. No oral switch option is allowed. Patients who withdraw from study drug dosing should perform all End of

Treatment (EOT) Visit procedures and should be followed through the Late Follow-up (LFU) Visit for safety assessments, even if they withdraw from dosing due to clinical failure.

Throughout the study, all patients will be monitored for signs and symptoms of cUTI or AP and the occurrence of adverse events. Laboratory data, including chemistry panels, complete blood counts, and samples for urine and blood cultures, as well as electrocardiograms (ECGs), will be collected from all patients at specified times throughout the study.

Sparse PK sampling (ie, a total of 5 samples per patient) will be performed to refine the population PK model. To maintain the blind, PK samples will be collected from both treatment groups. Samples obtained from the ETX2514SUL group will be analyzed using a validated assay by a central bioanalytical laboratory.

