#### **5.1.4.2. Per-Patient Microbiologic Outcome**

An overall per-patient microbiological response at Day 5, EOT, and TOC will be programmatically determined for each patient based on individual outcomes for each baseline pathogen. For a patient to have a microbiological response of eradication, the outcome for each baseline pathogen must be eradicated. If the outcome for any pathogen is persistence, the patient will be considered to have a microbiological response of persistence.

Microbiologic eradication: the outcome of all baseline pathogens must be eradication at the specified visit (Day 5, EOT or TOC).

Microbiologic persistence: the outcome of at least 1 baseline pathogen is persistence.

Microbiologic indeterminate: the outcome of at least 1 baseline pathogen is indeterminate and there is no outcome of persistence for any baseline pathogen.

An overall per-patient microbiological response at LFU will be determined for each patient and will be based on individual outcomes for each baseline pathogen. For a patient to have a microbiological response of sustained eradication, the outcome for each baseline pathogen must be sustained or presumed sustained eradication. If the outcome for any pathogen is recurrence, the patient will be considered to have an unfavorable microbiological response. A per-patient microbiologic outcome of persistence at TOC will be considered a per-patient continued persistence at LFU.

Sustained microbiologic eradication: the outcome of all baseline pathogens must be sustained eradication or presumed sustained eradication.

Microbiologic recurrence: the outcome of at least 1 baseline pathogen is recurrence.

Microbiologic continued persistence: a per-patient microbiologic outcome of persistence at TOC will be considered a per-patient continued persistence.

Microbiologic indeterminate: the outcome of at least 1 baseline pathogen is indeterminate and there is no outcome of recurrence for any baseline pathogen.

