## **8.2. Handling of Dropouts/Missing data**

For the primary efficacy outcome measure of overall response, patients with missing data or who are lost to follow-up will be considered as an indeterminate response and are included in the denominator for the calculation of overall success rate. Thus, patients with an indeterminate outcome are considered as failures for the primary analysis. A clinical failure occurring at an earlier time point will be carried forward to the subsequent visits.

In cases of missing or incomplete dates (e.g. AE and concomitant medications), the missing component(s) will be assumed as the most conservative value possible. For example, AEs with missing start dates, but with stop dates either overlapping into the treatment period or missing, will be counted as treatment-emergent, taking the worst-case approach. When partial dates are present in the data, both a partial start date and/or a partial stop date will be evaluated to determine whether it can be conclusively established that the AE started prior to the start of study drug or ended prior to the start of study drug. If the above cannot be conclusively established based on the partial and/or present dates, then the AE will be considered as treatment-emergent. Actual data values as they appear in the original eCRF will be presented in the data listings.

Missing values for other variables will not be imputed and only observed values will be used in data analyses and summaries.

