### **8.11.3. Analysis of Secondary Efficacy Endpoints**

The number and percentage of patients determined to be a clinical cure, clinical failure and indeterminate response at the TOC visit in the MITT, m-MITT, CE and ME Populations will be presented by treatment group. Two-sided 95% CIs for the observed difference in the clinical cure rates between the EXT2514SUL group and the placebo group (background imipenem/cilastatin therapy) will be presented based on a continuity-corrected Z-statistic.

The number and percentage of patients with a per-patient microbiologic eradication, persistence, and indeterminate response at the TOC Visit in the m-MITT and ME Populations will be presented by treatment group. Two-sided 95% CIs for the observed difference in the per-patient microbiological eradication rates between the EXT2514SUL group and the placebo group (background imipenem/cilastatin therapy) will be presented based on a continuity-corrected Z-statistic.

[Redacted content]

  

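### Only EOT persistence is carried to TOC, so a clinical failure without it who clears on a non-study antibacterial is scored as microbiologic eradication (secondary endpoint only)

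*Protocol*

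**What the plan says.** **Clinical side.** Protocol 7.6 states that "if a patient is a clinical failure at EOT, the patient is automatically considered a failure at the TOC and LFU Visits". SAP 8.2 is broader: "A clinical failure occurring at an earlier time point will be carried forward to the subsequent visits". Clinical failure includes new symptoms that need a non-study antibacterial, so the plan expects some failures to be treated with another drug before TOC.

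**Microbiologic side.** Protocol 7.8: "Per-patient microbiological response is determined programmatically based on the results of blood and urine cultures". SAP 5.1.4.2 builds the per-patient result from the per-pathogen results at the same visit. The one earlier result that overrides the TOC culture is EOT persistence: "Patients who are a persistence at EOT will be considered a persistence at TOC". Neither document's visible definitions refer to clinical failure or to non-study antibacterials when the TOC microbiologic outcome is scored.

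**Sampling.** Protocol 7.7 asks for a urine culture at scheduled visits and at "any time the patient is deemed to have failed while on therapy". Protocol 3.1 places the EOT visit on the last dosing day or the day after. Patients who stop dosing complete the EOT procedures and are followed to the Late Follow-up visit, "even if they withdraw from dosing due to clinical failure", although that follow-up is described as being for safety. Protocol 6.4 schedules a TOC urine culture and makes no exception for failures.

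**Use.** SAP 8.11.3 tabulates patients "with a per-patient microbiologic eradication, persistence, and indeterminate response at the TOC Visit in the m-MITT and ME Populations" and gives a 95% CI for the difference in eradication rates.

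**The concern.** A clear urine culture at TOC is evidence about the randomized regimen only if no other effective drug was given first. The plan accepts this in part: a patient persistent at EOT cannot become an eradication at TOC, whatever happens in between. It has no matching rule for a clinical failure in whom persistence was not recorded at EOT. If that patient takes a non-study antibacterial and the urine clears, the program assigns eradication.

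At stake is the stand-alone eradication rate at TOC in the m-MITT and ME Populations, which is a named secondary objective. The rate would be overstated in any arm that has such patients. The difference would be distorted if they form a larger share of one arm than of the other.

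**Working it through.** The documents give no power calculation or assumed eradication rate, so there is no planned figure to reproduce. The check applies the scoring rules as written and then sizes one misclassified patient.

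**Step 1: apply the rules to a patient rated clinical failure.** Inputs are the definitions in Protocol 7.4, 7.6 and 7.8 and SAP 5.1.4 and 8.2.

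| EOT microbiologic outcome | TOC culture | TOC microbiologic outcome | Overall response |
|---|---|---|---|
| Persistence | Clear | Persistence (carried) | Failure |
| Eradication | Clear | **Eradication** | Failure |
| Indeterminate or missing | Clear | **Eradication** | Failure |
| Eradication or indeterminate | Indeterminate | Indeterminate | Failure |
| Any | At or above threshold | Persistence | Failure |

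The composite is a failure in every row. The gap lies in rows 2 and 3 when a non-study antibacterial came before the TOC culture.

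**Step 2: how a patient reaches rows 2 or 3 after rescue.**
- Relapse between EOT and TOC. The EOT culture was clear, so there is nothing to carry. The culture required at failure covers failure on therapy only.
- An EOT culture that is missing or uninterpretable.
- An EOT culture taken after the new drug was started, which the next-day window allows.
- A clinical failure at EOT with a clear culture taken before rescue. This may be true on-drug eradication (see the objection).

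The cut-off also matters. EOT growth from 10^3 to below 10^4 CFU/mL is persistence, and so carried, under the EMA criterion but not under the FDA criterion.

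**Step 3: do the analysis populations remove these patients?** No. The CE and ME definitions (SAP 7.4, 7.5) do not mention non-study antibacterials. Beyond the m-MITT and CE criteria, ME asks only for a properly collected, interpretable TOC urine culture.

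**Step 4: size per patient.** About 80 patients at 2:1 gives 80 × 2/3 ≈ 53 and 80 × 1/3 ≈ 27. The share entering m-MITT is not stated; 60% to 100% is assumed.
- 100%: 1/53 = 1.9 points (ETX2514SUL); 1/27 = 3.7 points (placebo).
- 60% (n = 32 and 16): 1/32 = 3.1 points; 1/16 = 6.25 points.

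**Step 5: effect on the difference.** With k₁ and k₀ such patients in the two arms, the as-written difference departs from the corrected one by k₁/n₁ − k₀/n₀.
- One in placebo, none in ETX2514SUL: 0 − 1/27 = −3.7 points.
- Two and one: 2/53 − 1/27 = 3.77 − 3.70 ≈ +0.1 point. Both rates are overstated, but the difference is essentially unbiased.

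**Step 6: compare with precision.** The half-width of the continuity-corrected interval is 1.96 × √[p(1−p)(1/n₁+1/n₀)] + 0.5 × (1/n₁+1/n₀), taking the same assumed rate p in both arms.
- p = 0.9, n = 53 and 27: 1.96 × 0.0709 + 0.0280 = 16.7 points.
- p = 0.7, n = 32 and 16: 1.96 × 0.1403 + 0.0469 = 32.2 points.

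One or two misclassified patients are small against an interval of ±17 to ±32 points.

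**The case against.** **The central case is already covered.** A patient who fails on therapy has a urine culture at failure and all EOT procedures on stopping. If persistence is recorded at EOT, it stands at TOC. This is correct and it narrows the point to patients without recorded EOT persistence.

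**Other provisions may catch post-EOT relapses.** Non-study antibiotics for the infection are prohibited (Protocol 5.5.1), and needing a prohibited drug is a listed reason for discontinuation (4.3). A patient withdrawn after EOT completes the next visit at that time (6.6), so the TOC culture may fall close to the start of rescue. This helps only in part: withdrawal is discretionary, and nothing requires the sample to come before the drug.

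**The TOC culture may not be taken.** Follow-up after stopping is described as being for safety. If no culture is taken, the outcome is indeterminate and no error arises. Section 6.4 nevertheless schedules the culture for everyone.

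**Discordance is legitimate.** Clinical and microbiologic outcomes are separate components, and a clear EOT culture taken before rescue may show real eradication on study drug. This has force for the last route in step 2, and it is why the as-written scoring should be kept as a sensitivity analysis. It has little force for a relapse treated before TOC, or where no valid pre-rescue culture exists. Nor can the as-written rule be defended as a consistent policy of counting the TOC culture whatever was given, because the EOT-persistence rule already departs from that.

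**The consequence is limited.** The primary objective is safety, efficacy is descriptive, and no power is claimed. Text after SAP 8.11.3 is redacted, so a sensitivity analysis there cannot be excluded. All of this stands and keeps the point minor.

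**Conclusion.** The gap is real and narrow. A clinical failure without recorded EOT persistence, treated with a non-study antibacterial for the index infection before a clear TOC culture, is scored as eradication. No visible text prevents it. Each such patient moves an arm's rate by about 1.9 points (n=53) or 3.7 points (n=27) if everyone randomized is in m-MITT, and by more if fewer are. How many there will be cannot be derived from the documents. Severity: minor, secondary endpoint only.

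Three stronger readings are not supported:
- *That the microbiologic outcome is not carried forward at all.* Protocol 7.8 and SAP 5.1.4.1 carry EOT persistence to TOC.
- *That the primary efficacy result is exposed.* Clinical failure alone makes the composite a failure.
- *That the rule will mask or reverse a treatment benefit.* This needs proportionally more such cases in one arm. The documents give no rescue rates, no share of rescued patients with EOT persistence, and no clearance rate after rescue. A calculation that treats every rescued patient as eligible for eradication at TOC would also ignore the EOT-persistence rule and overstate the effect.

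**What to change.** In Protocol 7.8 and SAP 5.1.4, add a rule for a patient rated clinical failure who started a non-study antibacterial for the index infection before the TOC culture: a culture taken after that drug cannot establish eradication.
- If the last post-baseline culture before the drug was at or above the threshold (FDA and EMA criteria applied separately), or for a baseline blood pathogen the last blood culture was still positive, score persistence.
- Otherwise score indeterminate, kept in the denominator as a non-success, and extend the definition of indeterminate to include this case.
- A post-rescue culture that still grows the baseline pathogen at or above threshold stays persistence, as now.

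Report the as-written, culture-only scoring as a sensitivity analysis, with the number of patients per arm whose category differs between the two.

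**Cost.** One rule in each document and one extra table, settled before unblinding. Reported eradication rates become slightly lower, and some patients with true on-drug eradication will be scored indeterminate in the main analysis; the sensitivity analysis shows how many. A further urine culture at relapse between EOT and TOC would give better information, but it is optional and not needed for this fix.
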